4.4 Lifestyle Considerations

The site may contact subjects prior to study visits, as a reminder of the approaching scheduled visit and any applicable lifestyle restrictions.

4.4.1 Meals and Dietary Restrictions

From Screening (Visit 1) to the Subject's Last Study Visit

Property of Haleon- Confidential

May not be used, divulged, published or otherwise disclosed without the consent of Haleon

CCI [REDACTED] Abbreviated Clinical Protocol Template v1.0

Subjects should not chew gum or consume any confectionery containing xylitol (e.g., mints).

Before Clinical Efficacy Assessment Visits: Baseline (Visit 2) to Last Study Visit

Subjects must abstain from all food and drink (except water) for at least 4hrs prior to their scheduled assessment visits and until all assessments are complete during visit days. Water is permitted until 1 hour prior to their scheduled study visits.

4.4.2 Alcohol, Caffeine and Tobacco

Subjects should refrain from alcohol consumption for 24 hours before the clinical assessment visits.

4.4.3 Dental Product/Treatment and Oral Hygiene Restrictions

From Screening (Visit 1) to the Subject's Last Study Visit

- Subjects will not be permitted to use any oral care products (e.g., dentifrices, toothbrushes, mouthwash) other than those provided during the study.
- Subjects will not be permitted to use any dental floss, toothpicks, water floss, or interdental brushes (except for the removal of impacted food with nonantimicrobial products only).
- Subjects will be instructed to delay any non-emergency dental treatment until study completion (including dental prophylaxis). They will be required to inform site staff of any emergency treatment they receive during the study.

Before Clinical Efficacy Assessment Visits:

Subjects should refrain from oral hygiene procedures for 12 hours (+6 hours, -2 hours) before their visit, and attend the study site with overnight plaque growth.

4.4.4 Medication and Treatment Restriction

The following medication and treatment restrictions apply for the duration of the study:

- If current/ concomitant medications/ treatments or traditional herbal ingredients/ treatments are used during the study, their identity, as well as their dosage and frequency, start and stop dates must be reported to the Investigator and recorded in the CRF.

4.4.5 Contraception

There are no contraception requirements for subjects entered into this study. Females of childbearing potential should verbally confirm they are not currently pregnant or planning to become pregnant.

5 STUDY PROCEDURES

This section lists the procedures to be completed at each planned study visit. Each procedure is listed in [Table 5-1 Schedule of Activities](#)

Property of Haleon- Confidential

May not be used, divulged, published or otherwise disclosed without the consent of Haleon

CCI Abbreviated Clinical Protocol Template v1.0

Adherence to the study design requirements, including all procedures are essential and required for study conduct.

All information and data collected at each study visit will be documented in the CRF, unless stated otherwise.

5.1 Schedule of Activities

Table 5-1 Schedule of Activities

Procedure/Assessment	Study Visits				
	Visit 1 Screening		Visit 2 Baseline ¹ Day 0	Visit 3 Week 6 ¹ Day 42 (± 4)	Visit 4 Week 12 ¹ Day 84 (± 4)
Informed Consent	X	Washout period (14 - 28 days)			
Medical History	X				
Demographics	X				
Current/Prior/Concomitant Medication Review	X		X	X	X
Oral Soft Tissue (OST) examination	X		X	X	X
Oral Hard Tissue (OHT) examination	X				X
Gross Visual Assessment of Gingival Health	X				
Pocket Depth Assessment ²	X				
Inclusion/Exclusion Criteria	X		X		
Subject Eligibility	X		X		
Subject Continuance				X	X
Dispense Washout Toothpaste and Toothbrush	X				
Return Washout Toothpaste and Toothbrush			X		
Modified Gingival Index (MGI) Assessment			X	X	X
Repeat MGI Assessment ³			X	X	X
Expanded Bleeding Index (EBI) Assessment ⁴			X	X	X
Disclose Dental Plaque			X	X	X
Turesky Plaque Index (TPI) Assessment			X	X	X
Repeat TPI Assessment ⁵			X	X	X
Dental Prophylaxis			X		

Property of Haleon- Confidential

May not be used, divulged, published or otherwise disclosed without the consent of Haleon

CCI Abbreviated Clinical Protocol Template v1.0

Haleon

Clinical Protocol

Protocol Number: 300211

HALEON

Procedure/Assessment	Study Visits				
	Visit 1 Screening		Visit 2 Baseline ¹ Day 0	Visit 3 Week 6 ¹ Day 42 (± 4)	Visit 4 Week 12 ¹ Day 84 (± 4)
2 nd Clinician Check to Confirm TPI=0 (Additional Dental Cleaning Will Be Performed if Required)			X		
Stratification/Randomization			X		
Dispense Study Product(s), Toothbrush and Dosing Cups for Mouthwash ⁶ , Timer			X		
Dispense Additional Mouthwash and Dosing Cups ⁶				X ⁶	
Supervised Study Product Use			X	X	
Subject Brings Study Product(s) and Toothbrush to Site for Compliance Checks				X	X
Subject Returns Study Product to Site					X
Adverse Events (AEs) Review ⁷	X		X	X	X
End of Study Dental Prophylaxis (Optional)					X
Exit Satisfaction Survey: Subject-Completed NRS and Questionnaire ⁶					X ⁶
Study Conclusion/Subject Exit from Study					X

Footnotes:

- 1: Subjects will abstain from overnight toothbrushing for a minimum of 12hrs (+6hr, -2hr) immediately prior to the assessment visits (Visits 2, 3 and 4)
- 2: In relation to the general dentition inclusion/ exclusion criteria
- 3: Minimum one MGI repeatability assessments during each clinical assessment day; MGI repeatability assessment at Baseline visit will be conducted after the subject's eligibility has been confirmed.
- 4: NBS and bleeding sites% are derived from EBI assessment
- 5: Minimum one TPI repeatability assessments during each clinical assessment day; TPI repeatability assessment at Baseline visit will be conducted after the subject's eligibility has been confirmed.
- 6: Toothpaste/mouthwash treatment arm only

Property of Haleon- Confidential

May not be used, divulged, published or otherwise disclosed without the consent of Haleon

CCI

Abbreviated Clinical Protocol Template v1.0

7: Adverse Events (AEs), Serious Adverse Events (SAEs) and medical device incidents collected immediately after subject provides consent participate in the study by the completion of the Informed Consent Form (ICF).

5.2 Visit 1 / Screening

Screening procedures will be conducted by the Investigator (or suitably qualified designee), prior to randomization to study product. Where practically feasible, they should be completed in the order listed below.

1. Informed consent
2. Demographics, Medical history (including smoking) and prior/concomitant medication/treatment
3. OST examination
4. OHT examination
5. Gross gingival health assessment
6. Pocket depth assessment
7. Review of inclusion/exclusion criteria
8. Subject eligibility
9. Dispense washout toothpaste and toothbrush.
10. Record Adverse events & incidents

5.2.1 Informed Consent

The investigator (or designee) must obtain informed consent from each subject participating in this study after adequate explanation of the aims, methods, objectives, potential hazards of the study and their rights to refuse to enter the study or to withdraw from it at any time.

Informed consent must be obtained before any study-specific activity is performed. Two copies of the informed consent form (ICF) will be signed and dated by the subject, and the subject will be provided with one copy and the other will be kept at site.

If, during a subject's participation in the study, any new information becomes available that may affect the subject's willingness to participate in the study, each ongoing subject should receive a copy of this new information and be re-consented into the study. Each subject should be provided with a copy of the signed and dated amended consent form.

5.2.2 Demographics

The following demographic information will be collected: year of birth, sex at birth, race and ethnicity.

5.2.3 Medical History and Prior Medication/Treatment

Relevant medical and/or surgical history (in the last 1 year), including allergies or drug sensitivity and prior medications/treatments, including prescription and non-prescription drugs, dietary supplements and herbal remedies, taken in the last 30 days, that began before obtaining informed consent will be recorded as the Medical History/Current Medical Conditions.

5.2.4 Screening Assessments

The following procedures will be completed, and data recorded in the CRF. The following screening procedures should be carried out by a qualified dental professional:

- OST examination
- OHT examination
- Gross assessment of gingival health
- Pocket depth assessment

The oral examinations/assessments should be carried out as described in Section 6. All findings will be recorded in the CRF.

Findings from this examination performed at the Screening Visit will be used to determine subject eligibility.

5.2.5 Inclusion/Exclusion Criteria

Inclusion and exclusion criteria as per Section 4.2 and 4.3.

5.2.6 Subject Eligibility

The investigator and/or medically qualified designee will review inclusion/exclusion criteria, medical history, prior medications to confirm subject eligibility to participate in the clinical trial. This will be documented in the CRF.

To prepare for study participation, subjects will be instructed on the Lifestyle Guidelines and any Concomitant Medication/Treatment(s) requirements of the protocol.

5.2.7 Enrolled Subjects and Screen Failure

An enrolled subject is one who has agreed to participate in the clinical study following completion of the informed consent process directly or via their legally authorized representative and successfully met eligibility criteria to proceed beyond the screening visit.

Screen failures are defined as subjects who consent to participate in the clinical study but are not subsequently randomized.

To ensure transparent reporting of screen failure subjects, a minimal set of screen failure information will include demography, screen failure details (e.g., withdrawal of consent), eligibility criteria, any protocol deviations and any adverse events or incidents as applicable.

Individuals who do not meet the criteria for participation in this study (screen failure) may not be re-screened.

5.2.8 Dispense Washout Products

Eligible subjects will be provided with the washout toothpaste and toothbrushes to use during the washout period (14 -28 days). Subjects will be instructed to use only their supplied oral care products (washout products) according to their normal habit until their next appointment. Completion of all procedures will be documented in the CRF.

5.3 Visit 2 / Baseline (Day 0)

Subjects will visit the clinical study site 14 - 28 days after the Screening visit. The following procedures/ assessments will take place in the order listed below as much as possible and be recorded in the CRF:

1. Collect washout products returned by subjects to assess compliance.
2. Review of concomitant medication or non-drug treatments/procedures, adverse events, incidents and lifestyle restrictions
3. OST examination
4. MGI assessment
5. EBI assessment (including number of bleeding sites which is derived from EBI assessment)
6. Plaque disclosure
7. TPI assessment
8. Inclusion/exclusion criteria
9. Subject eligibility
10. MGI repeatability assessment (where applicable)
11. TPI repeatability assessment (where applicable)
12. Dental prophylaxis
13. 2nd clinician check to confirm TPI=0
14. Randomization
15. Dispense study products, toothbrush, dosing cups (toothpaste/mouthwash group only), and timer
16. Oral hygiene instructions
17. Supervised product usage at site
18. Record Adverse events & incidents

Changes in concomitant medication or non-drug treatments/procedures will be documented in the CRF.

Spontaneous reporting of adverse events and those elicited by asking subjects to respond to a non-leading question such as “How do you feel?” will be assessed and any AEs recorded in the CRF.

Property of Haleon- Confidential

May not be used, divulged, published or otherwise disclosed without the consent of Haleon

CCI [REDACTED] Abbreviated Clinical Protocol Template v1.0

5.4 Visit 3 / Week 6 (Day 42 ± 4 days)

The following procedures/ assessments will take place in the order listed below and be recorded in the CRF:

1. Collect study products returned by subjects to assess compliance. Also ask subjects about product usage compliance and remind them to follow product usage instructions.
2. Review of concomitant medications and non-drug treatments/ procedures, adverse events, incidents and lifestyle restrictions
3. Subject continuance
4. OST examination
5. MGI assessment
6. EBI assessment (including number of bleeding sites which is derived from EBI assessment)
7. Plaque disclosure
8. TPI assessment
9. MGI repeatability assessment (where applicable)
10. TPI repeatability assessment (where applicable)
11. Return study products to subject
12. Dispense additional mouthwash and dosing cups (Group toothpaste/mouthwash only)
13. Oral hygiene instruction
14. Supervised product usage at site
15. Record Adverse events & incidents

Changes in concomitant medication or non-drug treatments/procedures will be documented in the CRF.

Spontaneous reporting of adverse events and those elicited by asking subjects to respond to a non-leading question such as “How do you feel?” will be assessed and any AEs recorded in the CRF.

5.5 Visit 4 / Week 12 (Day 84 ± 4 days)

The following procedures/ assessments will take place in the order listed below and be recorded in the CRF:

1. Collect study products returned by subjects to assess compliance. Also ask subjects about product usage compliance.
2. Review of concomitant medications and non-drug treatments/ procedures, adverse events, incidents and lifestyle restrictions
3. Subject continuance

Property of Haleon- Confidential

May not be used, divulged, published or otherwise disclosed without the consent of Haleon

CCI [REDACTED] Abbreviated Clinical Protocol Template v1.0

4. OST examination
5. OHT examination
6. MGI assessment
7. EBI assessment (including number of bleeding sites which is derived from BI assessment)
8. Plaque disclosure
9. TPI assessment
10. MGI repeatability assessment (where applicable)
11. TPI repeatability assessment (where applicable)
12. Complete optional dental prophylaxis (as if deemed necessary by examiner)
13. Record adverse events & incidents
14. Exit Satisfaction survey (toothpaste/mouthwash treatment arm only)
15. Study conclusion

Changes in concomitant medication or non-drug treatments/procedures will be documented in the CRF.

Spontaneous reporting of adverse events and those elicited by asking subjects to respond to a non-leading question such as “How do you feel?” will be assessed and any AEs recorded in the CRF.

6 STUDY ASSESSMENTS

Every effort should be made to ensure that protocol-required tests and procedures are completed as described. However, it is anticipated that from time to time there may be circumstances, outside the control of the investigator that may make it unfeasible to complete an assessment. In these cases, the investigator must take all steps necessary to ensure the safety and well-being of the subject. When a protocol-required assessment cannot be performed, the investigator (or designee) will document the reason for the missed assessment as a protocol deviation and any corrective and preventative actions that he or she has taken to ensure that required processes are adhered to as soon as possible. The Sponsor must be informed of any missed assessments in a timely manner.

6.1 Screening Assessments

Screening assessments will be performed by appropriately trained staff/clinical examiners at the times, and in the order, defined in the **STUDY PROCEDURES** section of this protocol.

A single examiner will be responsible for the conduct of the clinical measures of gingivitis/plaque accumulation for the duration of the study.

Evaluable surfaces for clinical assessments will be identified by oral examination against the oral inclusion/exclusion criteria described in Sections 4.2 and 4.3 of this protocol. Ineligible subjects will not be re-screened.

Property of Haleon- Confidential

May not be used, divulged, published or otherwise disclosed without the consent of Haleon

CCI [REDACTED] Abbreviated Clinical Protocol Template v1.0

Assessments will be carried out by the investigator, or qualified designee, against the inclusion/exclusion criteria.

Findings from these examinations will be used to determine subject eligibility.

6.1.1 Gross Assessment of Gingival Health

Visual assessment of gingival health will be performed to record the presence/absence of plaque-induced gingivitis as per the inclusion criteria during Screening visit (Visit 1).

6.1.2 Pocket Depth Measurement

Pocket depth assessment will be performed during Screening visit. Michigan “O” probe with Williams Markings will be used as a "sensing" instrument to determine pocket depth. The probe tip will be inserted gently into the gingival sulcus or pocket and the total extent of the sulcus or pocket will be assessed.

6.2 Efficacy Assessments

The following efficacy assessments will be performed by appropriately trained staff/clinical examiners, at the times and in the order defined in the **STUDY PROCEDURES** section of this protocol.

If in the opinion of the examiner a subject is between defined grades/scores, a conservative approach should be used to provide the final score. The same approach should be applied throughout the study to ensure consistency in the grading of the scores at all timepoints.

6.2.1 MGI Assessment ([Lobene et al., 1986](#))

The MGI assessment is a non-invasive evaluation which focuses on the visual symptoms of gingivitis (for example, redness, texture, edema). The MGI will be assessed on the buccal and lingual marginal gingiva and interdental papillae of all scorable teeth (second permanent molar to second permanent molar in each arch) by an appropriately qualified examiner. Three scores will be recorded buccally/labially (papilla and margin) and three scores lingually/palatally (papilla and margin). The scoring of the MGI will be performed under dental office conditions using a standard dental light for illuminating the oral cavity.

The MGI scoring system will be as follows:

Table 6-1 Modified Gingival Index Scoring System

Score Description	
0	Absence of inflammation
1	Mild inflammation; slight change in colour, little change in colour; little change in texture of any portion of the marginal or papillary gingival unit
2	Mild inflammation; criteria as above but involving the entire marginal or papillary gingival unit

Property of Haleon- Confidential

May not be used, divulged, published or otherwise disclosed without the consent of Haleon

CCI Abbreviated Clinical Protocol Template v1.0

3	Moderate inflammation; glazing, redness, edema, and/ or hypertrophy of the marginal or papillary gingival unit
4	Severe inflammation; marked redness, edema and/ or hypertrophy of the marginal or papillary gingival unit, spontaneous bleeding, congestion, or ulceration.

The MGI will be assessed by the same examiner on all evaluable teeth from Baseline onwards as indicated in the Schedule of Activities.

6.2.2 EBI Assessment ([Van der Weijden et al., 1994a](#), [Van der Weijden et al., 1994b](#))

Gingival bleeding will be assessed according to the EBI, by inserting a periodontal probe into the gingival crevice and sweeping from distal to mesial around the tooth at an approximate angle of 60°, while in contact with the sulcular epithelium. Each of six gingival areas (distobuccal, midbuccal, mesiobuccal, distolingual, midlingual, and mesiolingual) around each tooth will be assessed. All scorable teeth in one quadrant should be probed first (approximately 30 seconds) before recording the number of gingival units which bleed.

The EBI scoring system will be as follows:

Table 6-2 Bleeding Index scoring system

Score	Description
0	No bleeding after 30 seconds
1	Bleeding observed within 30 seconds of probing
2	Bleeding observed immediately on probing

The EBI will be assessed by the same examiner on all evaluable teeth from Baseline onwards as indicated in the Schedule of Activities.

The number of bleeding sites for each subject at each visit is calculated as the number of evaluable tooth sites with a BI score of either 1 or 2.

Bleeding sites % = the number of bleeding sites / total sites examined

Repeatability exercise will not be performed for EBI.

6.2.3 Plaque Disclosure

Dental plaque is colorless and so is usually disclosed ('stained') prior to assessment. The disclosing solution will be used according to the manufacturer's instructions.

- At the request of the subject, the clinician may apply a thin layer of petroleum jelly to the subject's lips, as a barrier to help minimize staining by the disclosing solution. Care should be taken to ensure no petroleum jelly comes into contact with the labial surfaces of the anterior teeth as this could impact clinical assessments in this region.
- The subject will rinse their mouth with 10 mL tap water for 10 seconds to remove any food debris and expectorate.

Property of Haleon- Confidential

May not be used, divulged, published or otherwise disclosed without the consent of Haleon

CCI Abbreviated Clinical Protocol Template v1.0

- The clinician will then apply the plaque disclosing solution as per the label instructions. Care will be taken not to dislodge the plaque during this process. The subject will then rinse with 10 mL tap water for 10 seconds and expectorate to remove excess solution.

Plaque may be redisclosed between the TPI and repeat assessments at the discretion of the clinical examiner.

6.2.4 TPI Assessment ([Lobene et al., 1982](#))

TPI will be used to assess plaque on all gradable teeth meeting the inclusion/ exclusion criteria, and will be performed by an appropriately qualified examiner. Only natural teeth can be assessed. This means no crowns, bridges, and teeth with fillings (surface that has 50% of the surface gradable or no more than 50% of the surface filled) which, in the examiner's judgment, would prevent an accurate grading should be assessed. Third molars should not be assessed.

The plaque will first be disclosed using a plaque disclosing dye solution, in agreement with the manufacturer's instructions. The TPI will be assessed on the facial and lingual surfaces of each scorable tooth (second molar to second molar). Three scores should be recorded buccally/ labially (distal, body, mesial sites) and three scores lingually / palatally (distal, body, mesial sites).

Disclosed plaque will be scored as follows:

Table 6-3 Turesky Plaque Index Scoring System

Score	Description
0	No plaque
1	Separate flecks of plaque at the cervical margin
2	Thin continuous band of plaque (up to 1 mm) at the cervical margin
3	Band of plaque wider than 1 mm but covering < 1/3 of the tooth surface
4	Plaque covering \geq 1/3 but < 2/3 of the tooth surface
5	Plaque covering \geq 2/3 of the tooth surface

The TPI will be assessed by the same examiner on all evaluable teeth from Baseline onwards as indicated in the Schedule of Activities.

6.2.5 Repeatability Assessments

The clinical examiner selected for this study will have demonstrated their ability to replicate their own scores (intra-examiner repeatability/reliability) on a tooth site-by-tooth site basis in previous studies and/or calibration exercises. Repeat MGI and TPI assessments will be performed by the clinical examiner at Visits 2 - 4. At least 1 repeat assessment should be performed for each index on each clinical assessment day, that is, at least one MGI and one TPI repeat assessment on each assessment day. 'Repeat' subjects will be selected at random from those in attendance. Different subjects can be used for repeat MGI and TPI assessments.

Property of Haleon- Confidential

May not be used, divulged, published or otherwise disclosed without the consent of Haleon

CCI Abbreviated Clinical Protocol Template v1.0

At Baseline visit, MGI and TPI repeatability will be only assessed on subjects with confirmed study eligibility.

There should be a delay of at least 10 minutes between original and repeat assessments for a given subject and ideally separated by another subject. No other procedure on the subject should be carried out between the first and the repeat assessment. Where possible, the clinical examiner should assess a different subject in the intervening period.

Scores from the first assessment must not be visible to the examiner/scribe when the repeat assessment is carried out.

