## **4.6 Analysis of Other Variables**

### **4.6.1 Repeatability of the Examiner**

Repeat MGI and TPI assessments will be performed by the clinical examiners at Visits 2, 3 and 4. At least 1 repeat assessment should be performed for each index on each clinical assessment day 'Repeat' subjects will be selected at random from those in attendance on any given assessment day. Different subjects should be used for repeat MGI and TPI assessments. Due to the invasive nature of the EBI assessment, it is not feasible to conduct an accurate repeatability assessment for this index.

There should be a delay of at least 10 minutes between the original and the repeat assessment for a given subject; ideally, repeat assessments should be separated by another subject. No other clinical procedure should be carried out on the selected subject between repeat assessments.

Scores from the first assessment must not be visible to the examiner/scribe when the repeat assessment is carried out.

The repeat MGI and TPI assessments will be compared to the respective original assessments (excluding any tooth surfaces assessed as missing or not qualified). The repeat assessments will not be used in any efficacy analysis.

The first and second assessments of each index will be analyzed with a Fleiss-Cohen weighted kappa coefficient ( $\kappa$ ), along with the 95% CI, to assess the intra-examiner reliability. Reliability will be deemed:

- Excellent if  $\kappa > 0.75$
- Fair to good if  $0.4 \leq \kappa \leq 0.75$
- Poor if  $\kappa < 0.4$

This analysis will be conducted on each respective index repeatability population (MGI population and TPI population).

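### The visit lists place the repeat MGI after probing, plaque disclosure and TPI, while Protocol 6.2.5 and SAP 4.6.1 want nothing in between; if the lists are followed, the MGI kappa is not a pure measure of examiner repeatability

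*Protocol*

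**What the plan says.** Protocol 6.2.5 asks for at least one repeat MGI and one repeat TPI on each assessment day. First and repeat are to be at least 10 minutes apart, ideally with another subject seen in the interval. It adds: "No other procedure on the subject should be carried out between the first and the repeat assessment". SAP 4.6.1 has the same rule: "No other clinical procedure should be carried out on the selected subject between repeat assessments".

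The visit lists place the repeat MGI late. In Protocol 5.4 (Week 6) it is "9. MGI repeatability assessment (where applicable)", and in 5.3 (Baseline) it is "10. MGI repeatability assessment (where applicable)". In 5.5 (Week 12) it is also step 10. The lists for Weeks 6 and 12 open with the same sentence: "The following procedures/ assessments will take place in the order listed below and be recorded in the CRF". At Baseline the order is softer; steps take "place in the order listed below as much as possible and be recorded in the CRF". Protocol 6.2 sends the reader back to Section 5, because efficacy assessments are done "at the times and in the order defined in the" study-procedures section.

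A further condition applies at Baseline. Footnote 3 of Protocol Table 5-1 says "MGI repeatability assessment at Baseline visit will be conducted after" eligibility has been confirmed; SAP Table 1-1 and Protocol 6.2.5 agree.

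The repeat data go into a Fleiss-Cohen weighted kappa, labelled excellent above 0.75, fair to good from 0.4 to 0.75, and poor below 0.4 (Protocol 8.3.4, SAP 4.6.1).

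**The concern.** An intra-examiner kappa is meant to show how closely one examiner reproduces a score when the subject has not changed. MGI is a visual index of redness, texture and swelling. Between the two MGI scores the lists place a probe swept around each tooth in contact with the sulcular tissue, then a dye, then plaque scoring. The protocol itself calls EBI invasive and gives that as the reason for not repeating it. A second look at the gums after these steps may differ from the first for reasons unrelated to the examiner.

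A single examiner scores the whole trial, and EBI, the source of the primary endpoint, has no repeat. The MGI kappa is therefore the only reliability check on a gingival index made within the trial. If it came out low, nobody could tell whether the examiner or the sequence was responsible.

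**Working it through.** No figure in the documents depends on this point, so the check is a comparison of the step lists with the rule.

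**1. Step numbers (Protocol 5.3 to 5.5)**

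| Visit | First MGI | EBI | Disclosure | TPI | Repeat MGI | Repeat TPI |
|---|---|---|---|---|---|---|
| 2 (Baseline) | 4 | 5 | 6 | 7 | 10 | 11 |
| 3 (Week 6) | 5 | 6 | 7 | 8 | 9 | 10 |
| 4 (Week 12) | 6 | 7 | 8 | 9 | 10 | 11 |

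Three procedures on the subject separate the two MGI scores at every visit. Steps 8 and 9 at Visit 2 (criteria review and eligibility) are decisions, not procedures on the subject.

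**2. Visits 3 and 4.** The order is unqualified and Protocol 6.2 defers to it. Keeping to the list breaks 6.2.5; keeping to 6.2.5 breaks the list.

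**3. Visit 2.** The softer wording would allow a different order, but it does not help. The MGI repeat requires confirmed eligibility. Eligibility requires 10% to 30% bleeding sites, which come from EBI, and a mean interproximal TPI of at least 1.5 (Protocol 4.2). So EBI, disclosure and TPI must all precede the repeat MGI, and 6.2.5 cannot be met.

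**4. Analysis.** The MGI repeatability population is every subject with at least one repeat (Protocol 8.2.1, SAP 4.1.3). First and repeat values are pooled over tooth sites in one cross-table (SAP 4.6.1.1). Repeats taken after probing are neither flagged nor excluded, and SAP Table 5-1 does not mention the conflict.

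**5. TPI.** The listed order also puts the repeat MGI between the two TPI scores if one subject serves both indices. Protocol 6.2.5 says different subjects 'can' be used; SAP 4.6.1 says they 'should' be.

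**6. Direction of the effect, illustration only.** All inputs are assumed. True site scores 0 to 4 follow a wide distribution (15, 25, 30, 25, 5%) or a narrow one (5, 25, 50, 19, 1%). Each reading errs by one point, up or down with equal chance, with total probability 10% or 20%. Before the repeat, a share q of sites rises by one point. Scores are held within 0 to 4, and 400,000 sites were simulated. The statistic is kappa = 1 − Σw·O / Σw·E, with w = (i − j)²/16, O the observed cell proportions and E those expected from the margins.

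| Distribution, error | q = 0 | 10% | 20% | 30% | 50% |
|---|---|---|---|---|---|
| Wide, 10% | 0.931 | 0.900 | 0.870 | 0.841 | 0.787 |
| Wide, 20% | 0.870 | 0.842 | 0.815 | 0.790 | 0.742 |
| Narrow, 10% | 0.869 | 0.816 | 0.769 | 0.726 | 0.652 |
| Narrow, 20% | 0.767 | 0.726 | 0.689 | 0.654 | 0.595 |

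Kappa falls in every row. The label never changes in the first row. It changes only at q = 50% in the second, between 20% and 30% in the third, and below 10% in the fourth. The documents give neither q, the score distribution nor the error rate, so none of these rows can be taken as an estimate for this trial.

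**The case against.** The conflict in the text is hard to dispute. The case against making much of it has four parts.

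- **Use of the kappa.** Repeat data enter no efficacy analysis, study success rests on overall number of bleeding sites at Week 12, and no decision hangs on the bands. A downward bias would understate the examiner's reliability, which is the cautious direction. This stands and limits the importance of the point. It does not make a low kappa interpretable.
- **Mechanism.** MGI counts only spontaneous bleeding, and only at grade 4, so bleeding provoked by the probe is not a scoring criterion. This stands. The possible route is through the look of the tissue after probing and staining, and the documents do not say how large that effect is.
- **Other safeguards.** The examiner must already have shown site-by-site repeatability in earlier studies or calibration exercises (Protocol 6.2.5), and the SAP asks for different subjects for the two indices. Both stand. The first is evidence from outside this trial; the second protects the TPI repeat, not the MGI repeat.
- **Wording.** Both documents say 'should', which is weaker than a prohibition. That is so, but a rule that cannot be met at Baseline still needs correcting.

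A reader might go further and infer that the MGI reliability estimate is invalid, or that every MGI repeat is affected. The documents support neither. They do not show how much probing or dye changes a score, and a site that follows 6.2.5 at Visits 3 and 4 avoids the problem there.

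**Conclusion.** The inconsistency is real, it spans both documents, and at Baseline it cannot be avoided. If the listed order is followed, the MGI kappa reflects both examiner repeatability and any change caused by probing and dye, and it should not be graded against 0.75 and 0.4 as though it reflected the examiner alone. The bias is probably downward. That rests on the assumption that the intervening steps alter at least some visible scores. Its size is unknown, and a claim that kappa would fall by a stated amount or cross a band would rest on assumed inputs only.

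The consequence is confined to a quality measure. The primary analysis and the MGI efficacy analyses use first assessments and are untouched. The correction is worth making because it is cheap and removes an avoidable ambiguity from a planned result.

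**What to change.** - **Order.** In Protocol 5.3, 5.4 and 5.5 move the repeat MGI to after the first MGI and before EBI, at least 10 minutes later and ideally with another subject in between.
- **Baseline condition.** Remove the confirmed-eligibility requirement for the MGI repeat only, in Protocol 6.2.5 and in footnote 3 of Protocol Table 5-1 and SAP Table 1-1.
- **Population.** Keep the repeatability population as defined in Protocol 8.2.1 and SAP 4.1.3. Restricting Baseline repeats to randomized subjects is unnecessary and would contradict those definitions. State that both MGI scores are retained for a subject who then fails eligibility, since the minimum screen-failure data in Protocol 5.2.7 do not name them.
- **TPI.** Keep its repeat after TPI and, at Baseline, after the eligibility check, with no MGI repeat in between; the new order achieves this. Align Protocol 6.2.5 ('can') with SAP 4.6.1 ('should') on using different subjects for the two indices.

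Cost: changes to the step lists and footnotes, a wait of about 10 minutes for selected subjects, and a few Baseline repeats on subjects who turn out to be ineligible.
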